3.1 Sample Size Considerations

A suitable number of potential subjects will be screened in order that 55 subjects successfully meet the inclusion and exclusion criteria and continue into the Treatment Phase. Thirty subjects are expected to be enrolled in Cohort 1, approximately 10 in Cohort 2 and approximately 15 in Cohort 3. The sample size is not based upon statistical powering, but the number is considered to be sufficient to initially explore the endpoints and their relationship with SMT C1100 exposure.

Subjects who withdraw or who are withdrawn during the Treatment Phase may be replaced if the study has not yet reached full enrolment at the time of withdrawal. Subjects who withdraw or who are withdrawn due to an adverse event (AE) considered related to SMT C1100 will not be replaced.

Efforts will be made, in Cohorts 1 and 2, to balance the study populations and attempt to have at least 50% of boys with a fat: water fraction greater than or equal to 0.15. Efforts will also be made such that half of the boys are greater than or equal to 8 years of age. Such attempts will be made manually rather than via an automatic system; achieving these recruitment goals will be attempted but complete balance will not be enforced.

All subjects will be eligible to be rolled into the extension phase.

3.2 Randomization

Not applicable, as all study subjects will receive open-label SMT C1100.

4.0 Study Endpoints

4.1 Primary Endpoints

- Change from baseline to Weeks 12, 24, 36 and 48 in MRI leg muscle parameters (Cohorts 1 and 2)
- SMT C1100 and metabolite plasma concentrations at Weeks 1 (Days 1 and 7, as applicable (Cohorts 2 and 3 only)), 4, 8 (Cohorts 1 and 2 only), 12, 24, 36 and 48
- Safety data including:
 - Treatment emergent AEs

4.2 Secondary Endpoints

- Change from baseline to Week 24 or 48 in utrophin expression via muscle biopsy analysis (Cohorts 1 and 2)
- Change from baseline to Week 24 or 48 in muscle regeneration biomarkers via muscle biopsy analysis (Cohorts 1 and 2)
- Change from baseline to Weeks 12, 24, 36 and 48 (Cohorts 1 and 2) and from baseline to Weeks 1, 24 and 48 (Cohort 3) in pulmonary function tests
- Safety data including:
 - Vital signs (systolic and diastolic blood pressure and heart rate)
 - Physical examination
 - Twelve-lead electrocardiogram (ECG)
 - Echocardiogram (ECHO)
 - Pulmonary function tests:
 - Forced expiratory volume in 1 second (FEV₁)
 - Forced vital capacity (FVC)
 - Maximum inspiratory pressure (MIP)
 - Maximum expiratory pressure (MEP)
 - Peak expiratory flow (PEF)
 - Peak cough flow (PCF) (Cohort 3)
 - Sniff nasal inspiratory pressure (SNIP) (Cohort 3)
 - Safety laboratory evaluations (clinical chemistry, haematology, (all 3 Cohorts) coagulation (Cohort 2 and Cohort 3) parameters and urinalysis (all 3 Cohorts))

4.3 Exploratory Endpoints

- Change from baseline to Week 12, 24, 36 and 48 for Cohorts 1 and 2 and from baseline to Week 24 and 48 for Cohort 3 (in the main phase of the study) measured at 6-monthly intervals for the duration of the Extension Phase in 6MWD

- Change from baseline to Week 12, 24, 36 and 48 for Cohorts 1 and 2 and from baseline to Week 24 and 48 for Cohort 3 (in the main phase of the study) measured at 6-monthly intervals for the duration of the Extension Phase in North Star Ambulatory Assessment (NSAA) global score
- Change from baseline to Week 12, 24, 36 and 48 (in the main phase of the study) measured at 6-monthly intervals for the duration of the Extension Phase in timed function tests (10 meter run/walk, time to stand)
- Change from baseline to Week 12, 24, 36 and 48 for Cohorts 1 and 2 and from baseline to Week 24 and 48 for Cohort 3 (in the main phase of the study) measured at 6-monthly intervals for the duration of the Extension Phase in paediatric outcomes data collection instrument (PODCI) scores
- Change from baseline to Week 12, 24, 36 and 48 for Cohorts 1 and 2 and from baseline to Week 24 and 48 for Cohort 3 (in the main phase of the study) measured at 6-monthly intervals for the duration of the Extension Phase in Performance of Upper Limbs (PUL)
- Change from baseline to Week 12, 24, 36 and 48 (in the main phase of the study) and measured at 6-monthly intervals for the duration of the Extension Phase of blood biomarkers, e.g., creatine kinase, matrix metallopeptidase 9 and other biomarkers
- Change from baseline to Week 48 (in the main phase of the study) and measured at 12-monthly intervals for the duration of the Extension Phase in cardiac MRI parameters (Cohort 3)
- Change from baseline in MRI leg muscle parameters measured at 6-monthly intervals for the duration of the Extension Phase (Cohorts 1 and 2)
- SMT C1100 and metabolite plasma concentrations measured at 6-monthly intervals for the duration of the Extension Phase
- Change from baseline in pulmonary function tests measured at 6-monthly intervals for the duration of the Extension Phase

It should be noted that subjects in Cohort 3 may not be able to perform all of the functional tests at baseline. Therefore the subjects included in the analyses for these tests will be test specific and based upon their baseline ability to perform the test.

5.0 Definitions and Study Assessments

5.1 Definitions

Baseline

Unless stated otherwise, the baseline is defined as the last non-missing assessment prior to the first administration of investigational medicinal product (IMP). If the assessment time is missing while the assessment date is the same date as the first administration of investigation product, a scheduled pre-dose assessment will be considered as baseline.

Change from Baseline

Change from baseline is defined as (value at post-baseline visit – value at baseline). Similarly percentage change from baseline is defined as $100 \times (\text{change from baseline})/\text{baseline}$.

Concomitant and Prior Medication

Prior medications are defined as medications with a start date prior to first dose of IMP. Concomitant medications are defined as any medications ongoing at the start of IMP treatment or with a start date on or after the first IMP dose date. Consequently, medications ongoing at the start of IMP will be reported as both prior and concomitant medications.

Study Day 1

The first day IMP is administered.

Study Day

Study day is defined as the number of days from Study Day 1.

- Before Study Day 1, Study Day = (Date of Interest – Date of Study Day 1)
- On or After Study Day 1, Study Day = (Date of Interest – Date of Study Day 1) + 1

Therefore the day prior to Study Day 1 is Study Day -1.

Study Visit

For by-visit summaries, data will be assigned to visits using windowing (see below). If more than one actual visit (including the early termination or unscheduled visits) falls within the same defined window, the visit closest to the target day with non-missing data will be considered for analysis. If two actual visit dates are at the same distance from the target day, the latest visit with non-missing data will be considered for analysis.

| Study Analysis Visit | Target Day | Study Day | Interval (days) |
|--|--------------------------|----------------------------|-------------------------------|
| Baseline | 1 | ≤1* | NA |
| Day 7 (Cohorts 2 & 3 only) | 7 | 5 to 9 | 5 |
| Week 4 | 28 | 21 to 38 | 18 |
| Week 8 | 56 | 49 to 66 | 18 |
| Week 12 | 84 | 67 to 112 | 46 |
| Week 24 | 168 | 140 to 196 | 57 |
| Week 36 | 252 | 224 to 280 | 57 |
| Week 48 | 336 | 308 to 364 | 57 |
| Week 60 | 420 | 392 to 448 | 57 |
| Week W | W x 7 | (W x 7 -28) to (W x 7 +28) | 57 |
| And so forth for 3 monthly visits | | | |

* Must be prior to dosing if time of assessment is recorded.

Windowing will not be used for the biopsy data as there is only one measurement post dose.

These visit windows will be reviewed and may be updated. Any assessments that fall outside of these windows will be reviewed on a case-by-case basis, and decisions on their handling will be fully documented prior to reporting.

Data will be included in analyses regardless of the duration of time since their last dose of study treatment and the assessment. However additional summaries may be generated excluding subjects if their assessment is performed several weeks after their last prior study dose. This will be reviewed on a case-by-case basis as the decision will be dependent on the assessment and the likely impact of the exclusion on the interpretation of the results.

Data collected outside these windows will only be listed.

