Following single and multiple oral administrations, SMT C1100 was rapidly absorbed with time of maximum concentration (t_{max}) being attained within approximately 1–6 hours in all patients. SMT C1100 exhibited biphasic elimination with an apparent dose-independent terminal elimination half-life ($t_{1/2}$), with mean $t_{1/2}$ ranging from approximately 5–10 hours. Similarly to results seen in study SMT C11001 (conducted in healthy adults), single and multiple oral dose pharmacokinetics of SMT C1100 in male paediatric patients with DMD demonstrated large variability between patients and provided no evidence that increasing dose or differing dosing regimen had an impact on exposure. There was high between-patient variability (geometric coefficient of variation of 78–248%) in $AUC_{(0-t_{last})}$, area under the concentration curve from time 0 to the time of next dose ($AUC_{(0-\tau)}$) and C_{max} . The comparison of doses and regimens was hindered by this large variability and the presence of only four patients per group. Observed exposures were lower than anticipated with only a single patient receiving *bid* dosing achieving target exposures. Following 11 days of *bid* dosing, SMT C1100 exposure was significantly reduced, with systemic exposure (assessed by $AUC_{(0-\tau)}$) being approximately 56–65% lower on Day 11 compared to Day 1. A time-dependent reduction in exposure was observed in study SMT C11001, albeit not to the same magnitude (23–40% reduction) suggesting that SMT C1100 is subject to autoinduction, although AhR-mediated induction of CYP1A was not evident from *in vitro* evaluation.

In Study SMT C11002, the pharmacokinetic analysis of metabolites DHD I and DHD III obtained from an exploratory assay, revealed broadly similar disposition (t_{max} and $t_{1/2}$) to that of the parent drug. Both metabolites were markedly more abundant than SMT C1100 in plasma, with mean metabolite ratios appearing to be independent of dose. On Day 1, mean metabolite ratios ranged from 10.8–36.0 and 20.6–58.5 for DHD I and DHD III, respectively. Following multiple dosing, metabolite ratios were higher, ranging from 46.6–74.2 and 63.2–112 for DHD I and DHD III, respectively. As the exposure of DHD I and DHD III at 0.1 g/kg *bid* and *tid* doses was similar between Days 1 and 11, these data indicate that the increase in metabolite ratios are a reflection of a reduction in exposure to SMT C1100 over time.

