4.2.2. Individual Stopping Rules

The pharmacokinetics of SMT C1100 parent and metabolites, and their relationship with all safety parameters, will be reviewed on an ongoing basis by the Sponsor and the DMC. As this is an open-label study, the decision to stop individual patients may be made on a case-by-case basis. The DMC can also recommend, in individual patients, a lowering of the SMT C1100 dose.

If a patient's results meet either of the criteria below, dosing should be stopped and the tests should be repeated as soon as possible. If the repeated results still meet this criterion, the study drug will be permanently stopped and may not be restarted although the patient will continue to be followed for functional and MRI assessments for the duration of the study. If the patient is withdrawn from the study, a follow up visit should be arranged:

- GLDH \geq 3x ULN

Study Number: SMT C11005 Protocol	Compound No.: SMT C1100 Version: 5.0 24Feb2017
---	---

OR

- Bilirubin $\geq 2x$ ULN together with an INR $\geq 1.5x$ ULN (Cohort 2 and 3 only)

Any intolerable AE or SAE that is at least possibly related to study drug should lead to a temporary discontinuation of the patient's study treatment. After resolution of the intolerable AE or SAE, the Investigator, in discussion with the Sponsor, may decide to either permanently discontinue the patient's study treatment, or, if recommended by the DMC and Sponsor reinstate treatment but reduce their *bid* dose to 1.25 g for Cohort 1 and 3 or reduce the frequency to once-daily dosing (2.5 g or 1.25 g for Cohorts 1 and 3; 1 g for Cohort 2; see Section 8.1.1). If a lowered dose is tolerated for at least 2 weeks the Investigator can, based on the recommendation of the DMC and Sponsor escalate the dose up to the original strength. Once-daily dosing should occur in the morning.

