10.2. Patient Withdrawal

10.2.1. Patient Withdrawal from Investigational Medicinal Product

A patient will be withdrawn from treatment for any of the following reasons:

- Withdrawal of consent/assent to continue taking treatment
- The study Investigator or Sponsor, for any reason, decides the patient should be withdrawn from the treatment
- Adverse events, classed as possibly or probably related by the Investigator, which cannot be tolerated by the patient

If a patient is withdrawn from treatment where possible they should continue to attend all remaining study visits so that data can be collected. If patients will not assent or their parents/guardian will not consent to this then they should be withdrawn from the study.

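### The only on-treatment summary is optional, has no numeric cut-off, and depends partly on its expected effect on the results

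*SAP*

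**What the plan says.** SAP 5.1 (Definitions, under Study Visit) sets the default without discretion: "Data will be included in analyses regardless of the duration of time since their last dose of study treatment and the assessment". It then adds that "additional summaries may be generated excluding subjects if their assessment is performed several weeks after their last prior study dose". Whether this is done is settled case by case, because "the decision will be dependent on the assessment and the likely impact of the exclusion on the interpretation of the results". The section gives no number of days, no list of endpoints, no person responsible and no date for the decision.

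The protocol makes off-drug assessments likely. Under Protocol 4.2.2, when the liver stopping criteria are confirmed on repeat testing, study drug stops permanently but "the patient will continue to be followed for functional and MRI assessments for the duration of the study". Under Protocol 10.2.1, boys withdrawn from treatment for other reasons are asked to stay: where possible "they should continue to attend all remaining study visits so that data can be collected".

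**The concern.** A sensitivity analysis is informative because it is specified and shown whatever it says. Here, one of the two criteria for producing the on-treatment summary is how far it is expected to change the reading of the results. If it appears, the reader cannot tell whether it was chosen because it helped. If it is absent, the reader cannot tell whether it was judged irrelevant or unhelpful. The open cut-off adds a second free choice, since different readings of several weeks drop different boys.

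What is at stake is how far the mean changes in leg MRS, biopsy and functional measures can be read as changes on drug. Protocol 12.1.3 says that the sponsor will explore the open-label data regularly. SAP 7.0 schedules an interim analysis of Cohort 1 and 2 efficacy and pharmacodynamic data at Week 24. Those making the Week 48 choices could therefore already know the direction of the results.

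**Working it through.** The plan gives no figure to reproduce on this point. The check is a comparison of passages, followed by an illustration under stated assumptions.

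**1. Does another passage fix the choice?**
- SAP 5.1 requires decisions to be documented before reporting, but for assessments outside the visit windows.
- SAP 6.4 requires the same for exclusions from analysis populations, which is a different decision.
- Protocol 12.1.5 requires the clinical study report to give the reason when data are excluded. It does not cover a decision not to produce the extra summary.
- SAP 10.0 mentions a data access plan. As described, it governs who in the company sees the data; no rule for this choice is stated.

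None of these sets a cut-off, an endpoint list or a time for the decision.

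**2. Can off-drug values enter the analyses?** Yes, by three routes.
- Boys who stop drug continue follow-up (Protocol 4.2.2 and 10.2.1).
- A second biopsy may be taken at early termination (Protocol 4.1.1 and 6.2.1), and SAP 5.1 applies no visit window to biopsy data.
- SAP 5.2 has efficacy endpoints assessed at end of study, which the Time and Events Table places at Week 52 ± 2 weeks. The Week 48 window runs to Day 364 (52 × 7 = 364). If Week 48 is missing, an end-of-study value about four weeks off drug can stand in for it. Whether four weeks counts as several is not defined.

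**3. How far could the exclusion move a mean?**

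Inputs: n = 30 + 10 = 40 boys in Cohorts 1 and 2 (Protocol 5.1), pooled for leg MRI/MRS and function (SAP 9.6.1 and 9.7.1). Assumed, because the documents give neither: m boys are off drug at a visit, and their mean change differs from the rest by d SD, with a common SD.

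- Shift in the mean = (m/n) × d, in SD units.
- Standard error = 1/√n in SD units, with √40 = 6.325.
- Shift in standard errors = m × d/√n.
- 95% confidence interval half-width = t(0.975, 39)/√40 = 2.023/6.325 = 0.32 SD.

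| m | Shift, d = 1 | In SE, d = 1 | Share of half-width, d = 1 | Share of half-width, d = 0.5 |
|---|---|---|---|---|
| 2 | 0.05 SD | 0.32 | 16% | 8% |
| 4 | 0.10 SD | 0.63 | 31% | 16% |
| 8 | 0.20 SD | 1.26 | 63% | 31% |

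Biopsy groups are smaller because Week 24 and Week 48 are summarised separately (SAP 9.7.3.1). The planned Week 48 group is 22/2 + 4 = 15 boys (Protocol 4.1.1), and √15 = 3.873. With d = 1, excluding 1, 2 or 3 boys moves the simple mean change by 0.26, 0.52 or 0.77 SE.

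**4. What if either summary could be cited as favourable?** In 100,000 simulated trials with n = 40, no true change and off-drug boys no different from the rest, a one-sided 2.5% chance of a favourable interval became about 3.0%, 3.2% and 3.6% for m = 2, 4 and 8, per endpoint and visit. The SAP plans no formal test, so this only gives a sense of scale.

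**The case against.** The strongest reply is that the discretion covers very little. The all-data analysis is mandatory and the extra summary sits beside it, never in its place. A reader might infer that off-drug boys can be dropped from the main result, or that the more flattering version can be shown alone. SAP 5.1 supports neither, so a calculation of the bias from reporting only the better of two versions does not apply.

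Three further points stand:
- The type of assessment is the first criterion named, so the SAP does not ignore it. It only fails to give an interval for each type.
- The text speaks of likely impact and does not say when the decision is made. It would be wrong to claim that the cut-off is set after seeing the data; the plan simply does not prevent it.
- There is transparency elsewhere. SAP 9.2 counts, for each visit, the boys who had permanently stopped treatment. SAP 9.4.1 lists dosing regimens with start and stop days. SAP 9.1 lists all data with study days. A reader with the listings could rebuild an on-treatment summary.

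It can also be said that the objectives concern change following treatment, which the inclusive rule fits, and that the study is exploratory and unpowered (SAP 3.1). Both are true, and they support keeping the all-data analysis as main. They do not justify choosing the plan's own sensitivity summary partly by its expected effect.

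**Conclusion.** The point holds in a limited form. The main analysis is fixed and sound. The on-treatment summary is optional, has no numeric cut-off and is selected partly on expected impact, so it cannot serve as evidence of robustness. This is a stated rule that depends on the results, not merely missing detail.

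The effect is modest: 0.32 SE for two boys and 0.63 SE for four, at an assumed 1 SD difference and n = 40. It becomes large only if many boys stop drug, or in the small Week 48 biopsy group. The number off drug and the size of the difference are both assumptions.

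A reader might also argue from the mean half-life in Protocol 1.1.3, "ranging from approximately 5–10 hours", that weeks is plainly too long for ECG and laboratory data. That figure comes from study SMT C11002 with formulation F2, whereas this trial uses F3 and F6. It does not settle a cut-off here.

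**What to change.** Amend SAP 5.1 as follows.

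1. Keep the all-data analysis as main.
2. Delete the wording that makes the extra summary depend on its impact on the results.
3. Always produce, beside the all-data version, an on-treatment version of the leg MRS, biopsy and functional change summaries. Drop assessments, not whole subjects, made more than a fixed number of days after the last dose.
4. Set that number for each assessment type before results are reviewed. Twenty-eight days is one example; it is an analysis cut-off, not a figure from the documents and not a clinical rule.
5. Optionally, do the same for the by-visit ECG and laboratory change summaries, with the cut-off justified from F3 and F6 data. Leave unchanged the safety tables in SAP 9.8.3 and 9.8.5 that count events at any time after dosing starts.

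The cost is a short SAP amendment and a second run of existing tables. SAP 9.4.1 already uses dose dates, so no new data are needed. The downside is a few more tables.

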5.2 Efficacy Assessments

All of the efficacy endpoints will be assessed at baseline, end of study, and Weeks 12, 24, 36 and 48 during the first 48 weeks and then 6 monthly during the extension phase. If a subject withdraws from the study prematurely they will also be assessed at the termination visit.

The 6MWT will also be conducted at screening.

In the sections below reference is made to reasons for not performing an assessment or not completing an assessment. Different approaches will be taken for dealing with the missing data dependent on whether or not the reason is related to the subject's medical condition (i.e. informative). A reason of 'Subject physically unable' will be regarded as informative, whilst 'Site staff/facility unavailable' is not informative. Other reasons will require a team review on a case-by-case basis.

5.2.1 Six-Minute Walk Distance

The total distance walked during six-minutes will be recorded in the eCRF. Subjects in both Cohorts 1 and 2 are required to be ambulatory at Baseline. If the subject is unable to perform the assessment after Day 1 or is unable to complete it, the reason will be recorded. For an assessment not completed the duration of time walked will also be recorded.

If the reason given for not performing the assessment or not completing the assessment is related to the subject's medical condition (i.e. informative) the 6MWD will be taken as zero or the recorded 6MWD respectively. However, if the reason is not deemed to be related to their medical condition (i.e. non-informative) then the distance will be taken as missing.

The use of orthoses or aids will also be recorded. The 6MWD recorded will still be used in analyses, but the use of orthoses or aids will be summarized.

The number of falls or times the follower provides support will also be recorded. This will not impact the use of the 6MWD recorded, but will be summarized separately.

The %-predicted 6MWD will be calculated using the equation proposed by [Geiger \(2007\)](#):

Male 6MWD=196.72+ (39.81 x age) – (1.36 x age²) + (132.28 x height), where age is age at assessment (not integer age) in years and height is height at assessment in meters.

Changes from baseline will be calculated for 6MWD and %-predicted 6MWD. Baseline will be the average of the pre-dose measurements.

The following velocities of change (change per month) will also be calculated for both the 6MWD and the %-predicted 6MWD:

- Baseline to Week 12
- Week 12 to Week 24
- Week 24 to Week 36
- Week 36 to Week 48

And

- Baseline to Week 24
- Week 24 to Week 48

... and so forth when reporting the extension phase data

The time till a 10% reduction in 6MWD will be determined for each subject. The occurrence of this reduction will have to be confirmed by the next visit attended.

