5.2.2 North Star Ambulatory Assessment

The NSAA is a functional scale specifically designed for ambulant patients affected by DMD. It is designed to test 17 activities (see [Appendix 2](#)) with scores of 0, 1 or 2 for each activity; a higher score indicating fewer limitations due to DMD. The total score will be derived as the sum of the scores from the 17 activities, and hence has the range 0-34. If the NSAA was performed but some of the activity scores are missing, then the worst score of the adjacent visits will be used to calculate the total score. For example, if the Week 24 NSAA was performed but some of the activities were missing then the worst score for the corresponding activity at Week 12 and 36 will be used.

The NSAA linearized score will also be derived ([Mayhew 2013](#)) where the NSAA scale is converted to a 0-100 scale using 16 of the activities (excludes 'lifts head').

The time to rise from the floor (time to stand) and the 10-Metre run/walk time are also collected with this assessment and are described in sections below as independent endpoints.

If the subject is unable to perform the assessment the reason will be recorded. If the reason given for not performing the assessment is related to the subject's medical condition (i.e. informative) the activity score will be taken as zero, otherwise it will be taken as missing.

Changes from baseline in the total score and the linearized score will be calculated.

The following velocities of change (change per month) will also be calculated for the total and linearized scores:

- Baseline to Week 12
- Week 12 to Week 24
- Week 24 to Week 36
- Week 36 to Week 48

And

- Baseline to Week 24
- Week 24 to Week 48

... and so forth when reporting the extension phase data

Loss of ambulation will be determined by a score of 0 with the 'walk' activity in the NSAA. To ensure the subject's disease has truly reached this level, subsequent visits will also need to have a score of 0.

The number of functions (0, 1, 2...) a subject has lost ("unable"), compared to baseline, will also be determined at each visit. Again, to ensure, that the subject's disease has truly reached this level subsequent visits will also need to have a score of 0.

5.2.3 10-Metre Run/Walk

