5.2.6 Performance of the Upper Limbs

The PUL assessment (Version 2) was specifically designed to assess upper limbs in patients with DMD. It includes 22 items subdivided into high level shoulder (6 items), middle level elbow (9 items) and distal level wrist and hand (7 items) dimensions to test shoulder, elbow, and distal upper limb performance reflecting functional tasks (see [Appendix 4](#)). Prior to assessing these 22 items an entry level score (entry item) is determined. For weaker subjects, a low score on the entry item means high level items do not need to be performed with the shoulder dimension. Each item is scored on a 0-2 scale, except Items 15 and 22 which are scored as either 0 or 1. For all items a higher score indicates better performance. Each dimension will be scored separately with a maximum score of 12 for the shoulder level, 17 for the elbow level, and 13 for the distal level. A total score can be achieved by adding the three level scores (max global score 42).

If the subject is unable to perform the assessment the reason will be recorded. If the reason given is related to the subject’s medical condition (i.e. informative) the score will be taken as 0, otherwise the score will be taken as missing.

Changes from baseline will be calculated for each dimension and the total score.

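### A 6MWD, NSAA or PUL not performed for a temporary, non-DMD cause is scored 0 if recorded as 'Subject physically unable', and no summary without such zeros is planned

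*SAP*

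**What the plan says.** SAP 5.2 (Efficacy Assessments) bases the handling of missing tests on whether the reason relates to the boy's medical condition. It settles one reason in advance: "A reason of 'Subject physically unable' will be regarded as informative". Unavailable staff or facilities count as not informative. For the rest, "Other reasons will require a team review on a case-by-case basis".

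The zero rules follow from that classification:

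- **6MWD (SAP 5.2.1):** for an informative reason, "the 6MWD will be taken as zero or the recorded 6MWD respectively". A walk not performed becomes 0 m; a walk started but not finished keeps its distance.
- **NSAA (SAP 5.2.2):** if the assessment is not performed for an informative reason, "the activity score will be taken as zero, otherwise it will be taken as missing". If it is performed with some activities missing, the worse score from the adjacent visits is used.
- **PUL (SAP 5.2.6):** for an informative reason, "the score will be taken as 0, otherwise the score will be taken as missing".

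A missed visit is not imputed (SAP 9.1.1).

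Some outcomes need confirmation. For the 10% fall in 6MWD, "The occurrence of this reduction will have to be confirmed by the next visit attended". For loss of ambulation and number of functions lost on the NSAA, "subsequent visits will also need to have a score of 0". No such condition applies to means, changes from baseline, correlations or velocities (SAP 9.6 and 9.10). Velocities are planned for 6MWD and NSAA (SAP 9.6.2, 9.6.3) but not for PUL (SAP 9.6.7). The number of imputed values is tabulated (SAP 9.1), but no analysis without them is specified.

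**The concern.** The rule is meant to stop boys who lose function from dropping out of the averages, and for disease progression it does that. It has no exception for a boy who attends with, say, a limb in a cast and cannot do the test that day. If the site records 'Subject physically unable', he is scored as having no function, with no review.

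The plan shows in other places that short-term causes matter. The confirmation rules accept that one bad visit may not be disease. Protocol 5.2.1.2 excludes boys at entry for a lower limb injury that could affect the walk, and Protocol 6.5.5 places the PUL before any biceps biopsy. For the PUL, 0 is also a poor stand-in for temporary inability: under SAP Appendix 4, picking up one coin or briefly switching on a light already scores 1.

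There is no control arm and no powered test, so means, intervals, velocities and correlations are the efficacy result. One false 0 in about 40 boys can move them visibly, and not always against the drug: a 0 followed by recovery makes the later velocity look better. The same injury could also be 0 or missing, depending on whether the boy attended and which reason was recorded.

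**Working it through.** The plan states no figure to reproduce: the sample size is not powered (SAP 3.1). The check is the influence of one value.

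**Inputs from the documents**
- N = 30 + 10 = 40, since Cohorts 1 and 2 are pooled (SAP 3.1, 9.6.1). Cohort 3, about 15 boys, is summarised separately.
- Screening 6MWD of at least 300 m in Cohorts 1 and 2 (Protocol 5.2.1.1).
- Maximum scores: NSAA 34, PUL 42 (SAP 5.2.2, 5.2.6).
- A 12-week velocity is the difference in visit values divided by 3; a 24-week velocity is divided by 6 (SAP 9.6.1).

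**Assumptions not in the documents**
- The boy would otherwise have walked 300 to 400 m, or scored 20 to 34 (NSAA) or 30 to 42 (PUL).
- SD of 6MWD change 30 to 70 m; mean change -10 m.
- All 40 boys assessed, one affected.

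**Shift in the visit mean = -b/N**, where b is the value replaced by 0:

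| Measure | b | Mean shift | Shift in 12-week velocity, per month |
|---|---|---|---|
| 6MWD | 300 m | -300/40 = -7.5 m | -7.5/3 = -2.5 m |
| 6MWD | 350 m | -8.75 m | -2.9 m |
| 6MWD | 400 m | -10.0 m | -3.3 m |
| NSAA | 20 / 34 | -0.50 / -0.85 | -0.17 / -0.28 |
| PUL | 30 / 42 | -0.75 / -1.05 | none planned |

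In Cohort 3, with all 15 assessable, a boy at 300 m would move the mean by -300/15 = -20 m. The 300 m entry criterion does not apply to that cohort.

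**Recovery by the next visit.** One velocity falls by b/(3N) and the next rises by the same amount, so their difference moves by +2b/(3N): 2 × 300/120 = +5.0 and 2 × 400/120 = +6.7 m/month. For a 0 at Week 12 this falls in full on a planned contrast, Velocity (24-12) minus Velocity (12-B). For a 0 at Week 24, the planned contrast Velocity (48-24) minus Velocity (24-B) moves by 2b/(6N) = +2.5 to +3.3 m/month.

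**Confidence interval.** Half-width = t × SD/√40, with t = 2.023 on 39 df. Replacing one typical change of about -10 m by -350 m shifts the mean by -340/40 = -8.5 m:

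| Assumed SD of change | Half-width before | SD after | Half-width after | Median before → after |
|---|---|---|---|---|
| 30 m | 9.6 m | 61.6 m | 19.7 m | -10.0 → -11.9 m |
| 50 m | 16.0 m | 73.4 m | 23.5 m | -10.0 → -13.2 m |
| 70 m | 22.4 m | 88.3 m | 28.2 m | -10.0 → -14.4 m |

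**Velocity model.** The SAP's model (visit fixed, subject random) was fitted to one simulated set of 40 boys (baseline SD 50 m, residual SD 30 m). One Week 12 value of 329 m was set to 0 or to missing. Estimates ± 95% half-width, in m/month:

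| Week 12 value | Velocity (12-B) | (24-12) minus (12-B) |
|---|---|---|
| Real | -1.83 ± 4.14 | -1.34 ± 7.17 |
| Set to 0 | -4.57 ± 5.55 | +4.13 ± 9.62 |
| Set to missing | -1.57 ± 4.17 | -1.87 ± 7.24 |

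The shifts match the formula: -329/120 = -2.74 and +2 × 329/120 = +5.48, up to rounding. The pooled residual SD rises from 28.3 to 38.0 m, so velocities not involving Week 12 lose precision too: Velocity (36-24) stays at -2.86, but its half-width grows from 4.14 to 5.55.

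**Correlation.** SAP 9.10.4 plots 6MWD change against NSAA change with a Pearson coefficient. With truly unrelated changes in 40 boys (6MWD SD 30 to 70 m, NSAA SD 2 to 4 points, assumed), one boy at -350 m and -20 points gives a median r of 0.38 to 0.74.

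**The case against.** The strongest objection is that the trigger is inferred. The CRF is not among the documents, so neither its list of reasons nor its completion instructions can be seen. The governing test is whether the reason relates to the boy's medical condition, and an injury entered under another reason would go to team review. This stands in part: frequency and coding are unknown. But once 'Subject physically unable' is recorded, the text leaves no room for review.

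Second, much of the effect would be visible. Counts of imputed values, medians, quartiles, box plots, individual line plots, per-boy 6MWD/NSAA plots and listings are all planned, and the median moves only about 2 to 4 m. This stands and lowers the priority. It does not repair the means, intervals, velocities or correlations.

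Third, confirmation suits milestone events, while a visit mean describes that visit. This is a fair defence of the main rule. Making a visit's main value depend on recovery at the next visit would bring its own bias, and reclassifying bad outcomes in an open-label study adds discretion. The main rule should therefore stay, with the alternative as a repeat analysis.

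A reader might infer that every 'physically unable' record becomes 0, or that PUL zeros enter a velocity model. The documents do not support either: an incomplete walk keeps its distance, a partly completed NSAA borrows from adjacent visits, a missed visit is left missing, and PUL has no velocity analysis.

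**Conclusion.** The concern holds in a limited form. A 6MWD, NSAA or PUL that is not performed for a temporary, non-DMD cause, and is recorded as 'Subject physically unable', is scored 0 without review. That 0 enters means, 95% CIs and correlations for all three measures, and velocity models for 6MWD and NSAA only.

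For one affected boy in 40, the size is as worked above: -7.5 to -10 m on the 6MWD visit mean and, with recovery by the next visit, +5.0 to +6.7 m/month on the difference between successive velocities. These figures rest on the assumed value replaced and on complete data; the interval and correlation figures also rest on assumed SDs.

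It would go too far to conclude that the rule always works against the drug, since recovery produces a false gain, or that it undermines a test of success, since none is planned. The harm is to description of exploratory endpoints. Priority: minor to moderate.

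**What to change.** 1. In SAP 5.2, extend the case-by-case team review to 'Subject physically unable' records. Before each data cut, classify each record from the recorded reason and the AE data as DMD-related or as a documented temporary, non-DMD cause.
2. Keep the zero rule for the main summary.
3. Add to SAP 9.6 a repeat of the mean changes and 95% CIs (6MWD, NSAA, PUL) and of the velocity models (6MWD, NSAA) with the documented temporary-cause zeros set to missing. Give their number separately from the imputed count already planned.
4. At the Week 24 interim (SAP 7.0), where efficacy data stop at Week 24, show both versions and label zeros not yet confirmed.

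The cost is SAP wording, a small review step and one extra set of tables. No new patient procedure is needed. The classification involves judgement in an open-label study, so it should be documented before each cut; the main result does not depend on it.
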